### 8.4. Sample Subsets

The following sample subsets will be identified and included in the analysis of select outcomes.

- **Commercial vs. Medicare Supplemental-** Patients who meet all selection criteria and have Medicare Supplemental insurance at index will be classified as such.

- **Number of prior Biologics:** 0, 1, 2, 3+ at any time prior to index.
- **Pre-index MTX therapy:** Treatment with MTX prior to index medication.

### 8.5. Period of Observation

All patients will be required to be continuously enrolled in the health plan for at least 24 months. Patients will have a variable length baseline period of at least 12 months. The 12 months prior to the index date will be used to assess the majority of pre-index characteristics. However, for select measures, eg, number of prior biologic therapies, and years since first RA diagnosis, the entire variable length baseline period will be utilized.

Measures utilizing the variable length baseline are noted. All baseline periods will be censored at January 1, 2012. The twelve months following the index date will be used to assess outcomes including treatment patterns, and health care costs, utilization and medication effectiveness.

### 8.6. Variables

#### 8.6.1. Patient Characteristics

- **Index month/year-**The month and year of the patient's index date will be identified.
- **Age-**Age will be defined as of the index year.
- **Age groups-**Patients will be assigned to one of the following age groups: 18–44, 45-64, and 65+.
- **Sex-**sex will be captured from enrollment data; patients with undefined gender will be removed from the study sample.
- **Insurance type-**Whether the patient was covered under a commercial or Medicare Supplemental insurance plan will be captured.
- **Geographic region-**The United States (U.S.) region in which the study patient is enrolled in a health plan will be determined and reported and states will be categorized into five geographic regions: Northeast, North Central, South, West, Unknown.

#### 8.6.2. Clinical Characteristics

- **Pre-index biologic use-**The use of biologics during the pre-index period will be identified. In addition, indicator variables will identify the specific biologic(s) used during the pre-index period. A count will be created to identify the number of different biologics received during the baseline. These measures will be created during the 12 month baseline and during the entire variable length baseline period.

- **Pre-index NB-DMARD use:** The use of the 4 main NB-DMARDs (methotrexate, sulfasalazine, hydroxychloroquine, and leflunomide), and the other NB-DMARDs will be identified during the pre-index period. In addition, indicator variables will identify the specific medications used during the pre-index period. A count will be created to identify the number of different NB-DMARDs received during the baseline. These measures will be created during the 12 month baseline and during the entire variable length baseline period.
- **Pre-index Quan-Charlson comorbidity score-**A comorbidity score will be calculated based on the presence of diagnosis codes on medical claims in the 12-months pre-index period. The Quan-Charlson comorbidity score will also be categorized into the following groups: zero, one to two, three to four, and five or more.
- **Comorbid conditions**—General comorbid conditions will be defined using the Clinical Classifications Software managed by the Agency for Healthcare Research and Quality (AHRQ). This measure generates indicator variables for specific disease conditions based on ICD-9-CM diagnoses. The top 25 comorbid conditions identified during the pre- and post-index period will be presented.
- **Pre-index claims based index of RA severity (CIRAS):** The claims-based index for RA severity will be implemented. CIRAS provides a single value of severity using the following 9 measures.

---

 Clinical Classification Software (CCS) for ICD-9-CM. Agency for Healthcare Research and Quality, Rockville, MD. <http://www.hcup-us.ahrq.gov/toolssoftware/ccs/ccs.jsp>

Measure 	Score
Age (continuous)	-0.066
Gender 0: male 1: female	-0.092
Inflammatory marker test ordered 0: no 1: yes	0.60
Rehabilitation visit 0: no 1: yes	0.69
Rheumatoid factor test 0: no 1: yes	2.1
Felty's syndrome 0: no 1: yes	2.3
Number of platelet counts ordered 0 = 0 visits 1 = 1 visit 2 = 2 visits 3 = 3 visits 4 = 4+ visits	0.42
Number of chemistry panels ordered 0 = 0 panels 1 = 1 panel 2 = 2 panels 3 = 3 panels 4 = 4 panels 5 = 5+ panels	-0.14
Rheumatologist visit count 1 = 0 visits 2 = 1-4 visits 3 = 5+ visits	0.52
Intercept	6.5

- **Pre-index medications**-The most common medications used during the 12-month pre- and post-index periods will be identified. The most common 25 medications received will be identified.
- **Opioid, non-steroidal anti-inflammatory drug (NSAID) use**-The use of weak and/or strong opioids and/or non-steroidal anti-inflammatory drug (NSAID) during the 12-month pre- and 12-month post-index periods will be identified. The number of pharmacy claims for opioids and/or NSAIDs and the number of days from the index date to the first opioid and/or NSAIDs claim will be identified.

---

 Number of platelet counts, chemistry panels, and rheumatologist visits are counted 1 per person per day.

- **Opioid, NSAID use while persistent.** In addition to opioid/NSAID use during the follow-up, use of opioids/NSAIDs while persistent and after persistence will be identified in the 12-month follow-up period.
- **Corticosteroid use.** The use of oral corticosteroids during the 12-month pre- and 12-month post-index periods will be identified. In addition, the total prednisone-equivalent dose of oral corticosteroids will be calculated.
- **Pre-index visit with a rheumatologist.** A 0/1 flag will be created to determine if the patient had an ambulatory visits (office visit or outpatient visit) in which the physician was a rheumatologist in the 90 days before or on the index date. A separate variable will be created identifying the number of visits with a rheumatologist during the entire 12-month baseline. A flag will also be created identifying the presence of a rheumatologist visit in the entire variable length baseline and the number of visits in the variable length baseline.
- **Disease duration.** The number of days from the earliest claim with a diagnosis of RA in the variable length baseline until the index date will be identified. Disease duration will only be created during the variable length baseline.
- **Pre-index Out-of-pocket expenses.** The patient's total all-cause and RA-related out of pocket healthcare cost for healthcare services in the one year before the index date and during the entire variable length baseline period will be calculated.
- **Comorbidities of interest.** 0/1 flags will be created to identify the presence of the following comorbidities during the 12-month baseline period.
  - Cardiovascular diseases;
  - Chronic obstructive pulmonary disease (COPD);
  - Asthma;
  - Kidney disease;
  - Diabetes;
  - Depression;
  - Anxiety;
  - Liver disease;
  - Sleep disorders;
  - Hypertension;
  - Hyperlipidemia.

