### 8.2.1. Inclusion Criteria

This study will include individuals who are privately insured and with Medicare Supplemental insurance paid for by their employers and initiating tofacitinib in combination with MTX for RA between 01 January 2014 and 31 January 2017. To be included in the final study sample, patients must meet the following inclusion criteria:

1. At least one claim for tofacitinib between 01 January 2014 and 31 January 2017 (the identification period).

- a. **Medication index date.** The index date will be the date of the first claim for tofacitinib during the identification period.

*Note: Patients will have a variable length baseline of at least a year long. The baseline period will be censored at January 1, 2012 based on licensed data availability. The majority of baseline measures will use data from the 12 months immediately prior to the index date. Select measures will use data during the entire variable length baseline.*

- b. Tofacitinib initiation. Patients must have a 2nd claim for tofacitinib within 60 days of the end of the days supplied from their index claim (at least two claims with no 60 day gap).
- c. Oral MTX initiation. Patients must have an initial prescription for oral MTX in the period between 30 days prior to index date and 30 days following index date followed by a 2nd prescription for oral MTX within 60 days of the end of the days supplied from their initial MTX claim (at least two claims/administrations with no 60 day gap).

2. Presence of The International Classification of Diseases, 9th Revision, Clinical Modification (ICD-9 CM) code for RA (in any position) during the one-year pre-index period or on the index date. ICD-9 = 714.0x-714.4x & 714.81 or ICD10 = M05.\* & M06.0\*-M06.3\* or M06.8\*-M06.9\*.

3. At least 18 years old as of the index date.

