### **8.12. Limitations of the Research Methods**

#### **8.12.1. Claims**

Limitations that are general to claims database analyses and specific to this study should be noted. First, diagnosis of autoimmune conditions will be identified using ICD-10-CM diagnosis codes, which are subject to potential miscoding. Second, the baseline period for this study will be 12 months long. Therefore, patients treated with a biologic in the baseline can be considered to be continuing users of biologic therapy; however, patients with no biologic use in the baseline may have just been off therapy for the 12 months prior. Lastly, this study will include an examination of medication effectiveness at 1 year among all biologic users. Effectiveness will be measured using a validated algorithm; however, the algorithm was not validated for all medications being included. Specifically, tofacitinib was approved for treatment of RA after the algorithm was developed. This study will include consultation with physicians to determine if the algorithm is valid for all study medications or if modifications need to be implemented.

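### The general comorbid-condition (CCS) indicators are defined from ICD-9-CM codes only, although the plan expects ICD-10 codes in the same baseline window

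*Combined protocol and SAP*

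**What the plan says.** Section 8.6.2 defines the general comorbid conditions with the CCS and adds: "This measure generates indicator variables for specific disease conditions based on ICD-9-CM diagnoses". Footnote 3 to that section cites the tool as "Clinical Classification Software (CCS) for ICD-9-CM". No ICD-10 version or crosswalk is named for this measure. On reporting, the section says: "The top 25 comorbid conditions identified during the pre- and post-index period will be presented".

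Elsewhere the plan allows for both code systems. Inclusion criterion 2 (Section 8.2.1) defines RA by "ICD-9 = 714.0x-714.4x & 714.81 or ICD10" code lists, in the year before index or on the index date. Table 1 (Section 8.2.2) has an ICD-9 and an ICD-10 column for every exclusionary diagnosis, and exclusion criterion 1 applies the listed biologic-treated conditions over that same period. The limitations (Section 8.12.1) go the other way and name only the newer system: "diagnosis of autoimmune conditions will be identified using ICD-10-CM diagnosis codes".

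Section 8.6.2 contains two further comorbidity measures, the Quan-Charlson score and eleven 0/1 comorbidity-of-interest flags. Neither states a code version. Section 8.10.2 makes the Section 8.6.2 variables candidates for the multivariable models.

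**The concern.** The plan supplies both code systems where it selects patients and only one where it classifies their general comorbidities over the same period. A patient can enter on an ICD-10 RA code while no other diagnosis on ICD-10 claims is visible to the CCS measure.

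An unmapped code leaves the indicator at 0. It does not appear as missing, so the statement in Section 8.10.1 that missing data are not imputed would not bring the problem to light.

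Two things are at stake. The top-25 lists would under-count conditions to a degree that depends on calendar time. If baseline CCS indicators are used as covariates, they would be misclassified in the same way and would adjust less well. Adjustment matters here because Section 8.10.6 expects a fairly small sample with clearly different cohorts, and for that reason is wary of propensity matching.

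**Working it through.** The plan gives no figure on this point, so there is none to reproduce. The check is a count of calendar days.

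**Inputs from the documents**
- Identification period: 1 January 2014 to 31 January 2017 (Section 8.2.1), which is 365 + 365 + 366 + 31 = 1127 possible index dates.
- Baseline (Section 8.5): "The 12 months prior to the index date will be used to assess the majority of pre-index characteristics". Taken as the 365 days before index.
- Follow-up (Section 8.5): "The twelve months following the index date will be used to assess outcomes". Taken as 365 days starting on the index date, because Section 8.6.5 places index-date claims in the post-index period.

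**Assumptions, not in the documents**
- Index dates are uniform over the 1127 days.
- There is a single changeover date T, with only ICD-10 codes from T onward. T is varied from 1 January 2015 to 1 July 2016.

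**Formulas.** For index date x, the unreadable baseline days are min(365, max(0, x − T)) and the unreadable follow-up days are min(365, max(0, x + 365 − T)). Let M be the number of index dates on or after T. A run of partly affected dates contributes (1 + 2 + … + 364)/365 = 182 full-window equivalents. So:
- baseline share = (M − 365 + 182)/1127, for M of at least 365;
- follow-up share = (M + 182)/1127.

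**Worked case, T = 1 October 2015.** M = 92 + 366 + 31 = 489.
- Baseline wholly ICD-10: (489 − 365)/1127 = 124/1127 = 11.0%. Partly: 364/1127 = 32.3%. Unaffected: 639/1127 = 56.7%.
- Mean baseline days unreadable: (124 + 182)/1127 = 306/1127 = 27.2%.
- Follow-up wholly ICD-10: 489/1127 = 43.4%. Mean follow-up days unreadable: (489 + 182)/1127 = 671/1127 = 59.5%.

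**Range**

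| Assumed T | M | Baseline wholly ICD-10 | Baseline days unreadable | Follow-up wholly ICD-10 | Follow-up days unreadable |
|---|---|---|---|---|---|
| 1 Jan 2015 | 762 | 35.2% | 51.4% | 67.6% | 83.8% |
| 1 Jul 2015 | 581 | 19.2% | 35.3% | 51.6% | 67.7% |
| 1 Oct 2015 | 489 | 11.0% | 27.2% | 43.4% | 59.5% |
| 1 Jan 2016 | 397 | 2.8% | 19.0% | 35.2% | 51.4% |
| 1 Jul 2016 | 215 | 0% | 5.6% | 19.1% | 35.2% |

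In the last row M is below 365, so the baseline share is (0 + 1 + … + 214)/365/1127 = 63.0/1127 = 5.6%.

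**From days to indicators.** Days lost are not indicators lost. A condition coded once, on a random day, is missed with probability equal to the share of days unreadable. A condition coded often is missed only when the whole window is ICD-10. For T = 1 October 2015, if coding is spread evenly over the window, the loss of a baseline indicator lies between 11.0% and 27.2%, and of a follow-up indicator between 43.4% and 59.5%.

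**After the change.** With both mappings applied, no day in either window is unreadable for this reason.

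**The case against.** The strongest reply is that only one of three comorbidity measures is affected. The Charlson score and the eleven flags carry no ICD-9 restriction, so a patient with no CCS indicators may still have both. This stands. A reader might infer that patients indexed later will look free of comorbidity. The documents do not support that: the restriction is written for the CCS measure alone, and a straddling window leads to under-counting, not to zero.

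Second, a reader might infer that the study will report a false fall in comorbidity after index. Change from baseline is planned for costs and utilization counts (Sections 8.6.5 and 8.10), not for comorbid conditions. The comparison of pre- and post-index measures in Section 8.10.1 can be read as a comparison between cohorts. What remains is that the two top-25 lists are not comparable, because follow-up always lies later than baseline.

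Third, a reader might infer confounded cohort comparisons. That needs index dates to differ between the MTX cohorts, and nothing in the documents shows that they do. CCS indicators are only candidate covariates, and index month and year (Section 8.6.1) can also be entered. Post-index indicators are not baseline confounders, so the larger follow-up figures have no bearing on adjustment.

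Finally, programmers might load both mappings anyway. Section 8.11 says that analyses are programmed to the protocol's specifications, so doing this without a change of text would be an undocumented departure.

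**Conclusion.** The CCS definition is wrong as written, and this shows from the documents alone: Section 8.6.2 and footnote 3 conflict with inclusion criterion 2 and Table 1. The limitations sentence in Section 8.12.1 concerns autoimmune diagnoses. It shows only that ICD-10 coding is expected.

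The size is less certain. About 6-51% of baseline days and 35-84% of follow-up days would be unreadable to this measure, given uniform index dates and a changeover within the assumed range. These shares are an upper guide to the indicators lost.

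The consequence is calendar-dependent under-counting in descriptive output and weaker adjustment if baseline CCS indicators are used. No treatment-pattern, effectiveness or cost outcome is itself defined by these indicators. The Charlson score and the flags leave their code version open and are not shown to be wrong. The point deserves correction because it is a plain inconsistency that is cheap to remove.

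**What to change.** In Section 8.6.2 and footnote 3, state that CCS indicators use the ICD-9-CM mapping for ICD-9 claims and the corresponding ICD-10-CM mapping for ICD-10 claims, and cite both. The cost is one sentence, one reference and a second mapping table.

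Three optional additions:
- Name both code systems for the Charlson score and the comorbidity-of-interest flags, as a clarification only.
- Name both systems in the limitations sentence of Section 8.12.1.
- Tabulate the prevalence of the main CCS conditions by index quarter, so that any step at the changeover is visible before these variables are used in a model.

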#### 8.6.4. Medication Effectiveness

Among patients with at least one year of follow up, medication effectiveness at one year after the index date will be determined using the following six criteria. For each of the 6 criteria, a 0/1 flag will be created. Patients who are effectively treated for each of the 6 criteria will be considered effectively treated. Patients who fail any of the 6 criteria are therefore not effectively treated.

1. High adherence to index agent: a proportion of days covered (PDC) will be calculated based on total days supply over the 1 year follow-up. The PDC will be calculated by using the date of service and the day supply for each fill of the index medication. For patients that receive both 5mg and 11mg tofacitinb, both configurations will be treated interchangeably. Patients with early refills will be allowed to stockpile medications up to a maximum of 14 days total for later use.

---

 Curtis, J.R., et al., *Derivation and preliminary validation of an administrative claims-based algorithm for the effectiveness of medications for rheumatoid arthritis*. *Arthritis Res Ther*, 2011. **13**(5): p. R155.

 Oladapo, et. al. *Medication Effectiveness with the Use of Tumor Necrosis Factor Inhibitors Among Texas Medicaid Patients Diagnosed with Rheumatoid Arthritis*. *Journal of Managed Care Pharmacy*. 657 – 67. Vol. 20, No. 7. July 2014

2. No increase in dose for index medication compared to the starting dose. Dose escalation will be identified per the criteria listed in [Table 2](#).
3. No switching from the index medication to a (different) biologic agent or tofacitinib. A switch will be defined as use of a different biologic or tofacitinib any time during the follow-up period.
4. No adding of a new non-biologic DMARD to the index therapy. Adding a new non-biologic will be considered as having at least 1 claim for one of the 3 main:
  1. NB-DMARDs during follow-up and not having a claim for the same NB-DMARD during the baseline. Changing from 1 NB-DMARD at baseline to a different.
  2. NB-DMARD at follow-up will be considered as adding a new NB-DMARD, ie, failing the algorithm.
5. Oral glucocorticoids. Only National Drug Code (NDC) codes for oral glucocorticoids will be included:

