  - a. For patients with no claims for oral glucocorticoid prescriptions in the six months prior to the index date: cannot receive more than 30 days of oral glucocorticoids between (index date +91) to (index date + 359). 30 days of oral glucocorticoids will be determined by summing up the day supply of all glucocorticoids claims with a fill date between (index date +91) to (index date +359).
  - b. For patients with claims for oral glucocorticoids during the six months prior to the index date: No increase in oral glucocorticoid dose during months 6-12 after:
    - a. Index compared to the 6 months before the index date. Increase in oral glucocorticoids will be determined from the prednisone equivalent dose for all glucocorticoid claims filled during the respective time periods.
6. At most one parenteral or intra-articular glucocorticoid joint injection on unique days after the patient had been on biologic treatment for more than three months between (index date +91) to (index date +359).

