### **8.10. Data Analysis**

#### **Primary Objective**

- **To compare treatment patterns including dosing, concomitant medication use, adherence, persistence and switching** among tofacitinib+MTX patients who discontinue MTX vs. persist with MTX or experience interrupted MTX.

For this objective, treatment patterns will be summarized across the cohorts of interest. Specific treatment patterns include non-persistence with the index medication, receipt of an opioid, receipt of an NSAID, adherence with the index medication, adherence with MTX.

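### Follow-up opioid and NSAID receipt, a primary-objective treatment pattern, is compared across MTX cohorts with no specified split by, or adjustment for, baseline use of the same class.

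*Combined protocol and SAP*

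**What the plan says.** Section 8.6.2, in the item on opioid and NSAID use, states: "The use of weak and/or strong opioids and/or non-steroidal anti-inflammatory drug (NSAID) during the 12-month pre- and 12-month post-index periods will be identified". It adds a count of pharmacy claims, and says that "the number of days from the index date to the first opioid and/or NSAIDs claim will be identified". The next item says that "use of opioids/NSAIDs while persistent and after persistence will be identified in the 12-month follow-up period"; section 8.6.3 defines persistence for the index medication.

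Section 8.10 turns these measures into outcomes. Under the primary objective, "treatment patterns will be summarized across the cohorts of interest", and the patterns then listed include "receipt of an opioid, receipt of an NSAID".

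Other sections bear on the point:
- Section 8.10.1 plans bivariate tests of pre-index and post-index measures by cohort. It also says in general terms that multivariable techniques will be used to compare outcomes.
- Section 8.10.2 limits multivariable work to selected objectives. Its list of possible model outcomes covers costs and medication effectiveness. Every variable in sections 8.6.1 and 8.6.2 is a candidate covariate.
- Section 8.10.6 expects a fairly small sample and cohorts that differ clearly.
- Section 8.8 gives no sample size calculation.

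For some other drugs, section 8.6.4 does use baseline information. An added NB-DMARD counts only in a patient "not having a claim for the same NB-DMARD during the baseline". The oral glucocorticoid criterion has separate rules for prior users and non-users, the first of which begins "For patients with no claims for oral glucocorticoid prescriptions in the six months prior to the index date".

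**The concern.** Receipt in the 12 months after index combines three quantities: how many patients used the class before index, how many of those continue, and how many of the rest start. Only the last two can reflect what happens after index. A patient who refills a long-standing NSAID counts the same as one who starts an NSAID in follow-up.

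The number of days from index to a claim has the same mixture. In a baseline non-user it is time to starting the class. In a baseline user it may largely reflect refill timing.

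What is at stake is the concomitant-medication part of the primary objective. A cohort difference in receipt could be read as a difference in need for symptomatic treatment when it only carries forward a difference that existed before index. A real difference in starting could also look smaller than it is.

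**Working it through.** The plan states no pre-index, continuation or new-use rate, no cohort size and no significance level, so it has no figure to reproduce. Every number below is an assumption, used to show how the mechanism works and how far it could range.

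**Formula.** In one cohort, let p be the proportion with a baseline claim for the class, c the proportion of those with at least one follow-up claim, and i the proportion of baseline non-users who start. Then

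receipt = p × c + (1 − p) × i.

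**1. Unequal baseline, no post-index difference.** If c and i are the same in both cohorts, the difference in receipt is (c − i) × (p₁ − p₂), so the fraction of the baseline gap carried over is c − i. With c from 0.5 to 0.9 and i from 0.1 to 0.3:
- smallest: 0.5 − 0.3 = 0.2
- largest: 0.9 − 0.1 = 0.8

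**2. Example with baseline use of 60% versus 45%.** The last two columns give the chance that an unadjusted two-sided 5% test of two proportions is significant although nothing differs after index.

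| c, i | Receipt | Difference | Odds ratio | 100 per cohort | 200 per cohort |
|---|---|---|---|---|---|
| 0.5, 0.3 | 42% v 39% | 3 points | 1.13 | 6% | 9% |
| 0.7, 0.2 | 50% v 42.5% | 7.5 points | 1.35 | 18% | 32% |
| 0.9, 0.1 | 58% v 46% | 12 points | 1.62 | 40% | 67% |

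**3. Equal baseline, real difference in new use.** With c equal in both cohorts, the difference in receipt is (1 − p) × (i₁ − i₂). For new use of 30% versus 20%:
- p = 0.3: 0.7 × 10 = 7 points
- p = 0.5: 0.5 × 10 = 5 points
- p = 0.7: 0.3 × 10 = 3 points

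**4. Share of follow-up users who are continuing users.** This is p × c / [p × c + (1 − p) × i]. With p from 0.3 to 0.7 it runs from 0.15/0.36 = 0.417 (p = 0.3, c = 0.5, i = 0.3) to 0.63/0.66 = 0.955 (p = 0.7, c = 0.9, i = 0.1).

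**5. Effect of splitting or adjusting.** Take p = 0.50 versus 0.35, c = 0.80 and i = 0.15. Receipt is 0.50 × 0.80 + 0.50 × 0.15 = 0.475 versus 0.35 × 0.80 + 0.65 × 0.15 = 0.3775, a gap of 0.0975 = 0.65 × 0.15. Among baseline users it is 0.80 in both cohorts; among non-users it is 0.15 in both. The cohort odds ratio is 1 in each stratum, so a logistic model with cohort and the baseline flag also gives 1. The spurious gap disappears.

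**6. Whether the plan already does this.** The primary-objective text names only a summary. The subgroup analyses in section 8.10 use insurance type, regimen and number of prior biologics, not prior opioid or NSAID use. Receipt is absent from the possible model outcomes in section 8.10.2.

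**The case against.** The strongest reply is that the plan is not blind to baseline use. Section 8.10.1 would put pre-index and post-index use side by side by cohort, so a careful reader would see an imbalance. Section 8.10.2 makes pre-index use a candidate covariate, its outcome list is open, and section 8.10.1 promises multivariable comparison in general terms. The objective speaks of medication use rather than initiation, so prevalence of use is a legitimate thing to describe.

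Much of this stands. It means an imbalance would be visible and could be adjusted for. But two marginal percentages do not give starting or continuation rates, and nothing commits the analysis to adjusting receipt. Section 8.10.2 confines multivariable work to selected objectives as already described, and the primary-objective text describes none.

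A reader might also infer that the plan contradicts itself by handling NB-DMARDs and glucocorticoids differently. That goes too far. Those rules belong to a cited effectiveness algorithm, and section 8.6.2 records oral corticosteroid use in the two windows without a prior-use split, as it does for opioids and NSAIDs. The rules show that the distinction is available to the plan, not that a general rule was broken.

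Nor does the plan make it impossible to identify patients who stop: the two flags, cross-tabulated, find them. And the days from index to a claim in a baseline user need not be leftover supply, since the baseline claim may be many months old.

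**Conclusion.** The point holds in a limited form. As specified, the cohort comparison of opioid and NSAID receipt is open to confounding by baseline use of the same class, and it dilutes a difference in new use even when baseline use is balanced. No specified analysis separates or corrects this.

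The size cannot be determined from the documents. The carry-over of 20% to 80% rests wholly on the assumed ranges for continuation and new use, and the rejection rates also on an assumed 15-point baseline gap and assumed cohort sizes. The expectation in section 8.10.6 that the cohorts differ is general and says nothing about prior opioid or NSAID use.

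A reader might infer that the comparison mostly reproduces pre-index use, or that adjusting a model of receipt would not help. The documents support neither. Carry-over could be minor or dominant, and adjustment for the baseline flag removes the spurious gap when continuation and new use are equal across cohorts. What a main-effect adjustment does not do is show starting and continuing separately. This is a low-cost improvement to a named primary-objective measure.

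**What to change.** In sections 8.6.2 and 8.10, separately for opioids and for NSAIDs:

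1. Report and compare follow-up receipt by baseline use of the same class in the 12 months before index: new use among baseline non-users, and continued or discontinued use among baseline users.
2. Give one overall cohort comparison of receipt adjusted for the baseline-use flag. The logistic model in section 8.10.4 will serve.
3. Compute the days from index to claim in baseline non-users only, or report it separately by baseline use.
4. Keep overall receipt as a description.
5. State that new use is counted from the tofacitinib index date. A start may precede the MTX gap, so it should not be described as use begun after MTX withdrawal.

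No new data are needed; both windows are already captured, and the work is plan wording, a cross-tabulation and one model per class. The cost is wider intervals within strata and possibly sparse cells, since section 8.3 already foresees merging cohorts if numbers are short. If cells are sparse, the adjusted overall comparison is the fallback.
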